## Secondary Outcomes Assessment

**1. Montgomery-Asberg Depression Rating Scale (MADRS):** The MADRS (Montgomery & Asberg, 1979) is a clinician-rated instrument that measures the presence and severity of depression. The MADRS has demonstrated very good reliability and validity in clinical applications (Cusin et al., 2009). This instrument consists of a 10-symptom scale. Each symptom is rated on a defined step scale (0 to 6). A high numeric rating reflects a greater degree of symptom severity. This outcome will be assessed by the mean change from baseline MADRS score.

**2. Hamilton Anxiety Rating Scale (HAM-A):** The HAM-A is a clinician-rated instrument that measures the presence and severity of anxiety. The HAM-A has demonstrated adequate psychometric properties (Riskind et al., 1987). This instrument consists of a 14-symptom scale. Each symptom is rated on a defined step scale (0 to 4). A high numeric rating reflects a greater degree of symptom severity. This outcome will be assessed by the mean change from baseline HAM-A score.

**3. Sheehan Disability Scale (SDS):** The Sheehan Disability Scale (SDS) (Sheehan, 1983) is a patient-rated instrument designed to assess the impact of perceived problems on work productivity, social/leisure activities, and family life/home responsibilities. The SDS has demonstrated adequate psychometric properties (Frischholz et al., 1990). The Sheehan Disability Scale consists of 3 questions rated on a visual analog scale (0 to 10). Higher scores represent greater impairment of activity. This outcome will be assessed by the mean change from baseline SDS score

**4.PTSD Checklist (PLC-C):** The PCL-C (civilian) is a 17-item self-report measure of the 17 DSM-IV symptoms of PTSD used for screening individuals for PTSD, diagnosing PTSD, and monitoring symptom change during and after treatment. It asks about symptoms in relation to "stressful experiences" and can be used with any population and has demonstrated adequate psychometric properties (Weathers et al 1994).

**5.UKU Side Effect Rating Scale, Self-rating version:** The UKU side effect rating scale, self-rating version (UKU-SERS-Pat) (Lingjaerde et al., 1987), a patient-rated scale, is a valid and reliable comprehensive measure to evaluate side effects of psychotropic medications (Lindstrom et al., 2001). Adverse events in the psychic, neurologic, autonomic, dermatological, and sexual domains will be assessed. For symptoms endorsed as present, a clinician will further assess their severity, potential causal relationship with the medications, and interference with daily performance.

**6.Additional secondary outcome measures:** These will include evaluating changes in N-acetyl aspartate (NAA) levels in the hippocampus and anterior cingulate cortex following riluzole or placebo administration measured using magnetic resonance spectroscopy (H MRS) among a sub-sample of WRNMMC participants.

### Acute Trial Assessments

As shown in **Section 5.5.8 Study Time Line**, subjects participating in this study will be rated weekly during the double-blind phase for severity of PTSD using the same scales as were obtained at Visit 2. Week 8 or Visit 9 ratings will be used to determine whether patients meet criteria for response. Side effects will be assessed using the UKU side effect rating scale, self-rating version (Lindstrom et al., 2001).

### Additional Measurement Instruments

**1.Liebowitz Social Anxiety Scale (LSAS):** A 24-item scale providing separate scores for fear and avoidance in social and performance situations over the past week (approx. 8 minutes to complete) (Liebowitz, 1987). This measure has demonstrated adequate psychometric properties (Fresco et al. 2001).

**2.Pittsburgh Sleep Quality Index (PSQI):** A 19-item instrument to assesses sleep quality and disturbances over a 1-month time interval (approx. 5 to 7 minutes to complete) (Buysse et al. 1989). The PSQI had demonstrated acceptable psychometric properties (Carpenter & Andrykowski, 1998).

**3.Dissociative Experience Scale (DES):** A 28-item questionnaire used to screen for dissociative symptoms (approx. 8 minutes to complete) (Bernstein et al. 1986). The DES has demonstrated excellent reliability and validity (Frischholz et al., 1990).

**4.World Health Organization Quality of Life (WHOQOL-BREF):** is a self-report measure of quality of life, life satisfaction and personal well-being (Murphy et al., 2000). 26-items assess the broad domains of physical health, psychological health, social relationships and environmental factors (e.g., finances, safety). This measure has strong psychometric properties (Skevington et al., 2004) and will be administered at each time point. The overall QOL score will be used as the QOL outcome measure.

**5.Connor-Davidson Resilience Scale (CD-RISC):** A 25-item scale of ability to recovery after a traumatic event (approx. 8 minutes to complete) (Connor & Davidson, 2003). The CD-RISC has demonstrated good psychometric properties (Windle et al., 2011).

**6.Childhood Trauma Questionnaire, Short Form (CTQ-SF):** A 28-item measure of childhood physical, sexual and emotional abuse and physical and emotional neglect (approx. 8 minutes to complete). The CTQ-SF has demonstrated good reliability and validity (Bernstein et al 2003).

**7.Symptom Checklist, 90 items, Revised (SCL-90-R):** A 90-item instrument to evaluate a broad range of psychological problems and symptoms of psychopathology. The instrument is also useful in measuring patient progress or treatment outcomes (approx. 12-15 minutes to complete) (Derogatis, 1999). The SCL-90-R has demonstrated adequate psychometric properties (Hardt et al., 2000).

**8.Peri Traumatic Distress Inventory (PDI):** A 13-item self-report measure to obtain a quantitative measure of the level of distress experienced during and immediately after a traumatic event (approx. 5 minutes to complete). The PDI has also demonstrated good reliability and validity (Brunet et al 2001).

**10.3 At any point in the study, will you request, use, or access PII from the Military Health System (MHS)?**

Yes  No

**10.4 Have you consulted with an MHS data expert to determine the data elements to be extracted or the information system(s) to access?**

Consulting with a data expert often saves time later in the compliance process because the data expert can advise on the data available in the numerous MHS information systems, the quality of that data and the methods for encrypting and collapsing data. To schedule a consult with an MHS data expert, send an email to: ([[contact]](mailto:[contact]))

Yes, then complete the questions below according to the data consult  
 No, then complete the questions below according to the best of your knowledge (NOTE: It is highly recommended that you work with an MHS data expert)

**10.5 Indicate whether you plan to receive a data extract from the MHS or plan to access an information system directly to create a data set:**

A data extract is when the MHS or a contractor provides the data set directly to the researcher. When receiving a data set through data extract, the researcher may indicate whether the data elements should be provided as is, encrypted or collapsed. In contrast to a data extract, access to an information system means that the researcher may directly access an MHS information system and create a data set for the research study

Data Extract  
 Access

**10.6 Do you intend to use only de-identified data from the MHS in your research study?**

There are different two methods for de-identifying data pursuant to HIPAA:  
 1) Safe Harbor Method: Removing all of the identifiers listed in Table 1 below, provided that the researcher does not have actual knowledge that the remaining data can be used alone or in combination with other information to identify the individual who is the subject of the information  
 2) Statistical Method: An expert, with appropriate knowledge of and experience with generally accepted statistical and scientific principles and methods for rendering information not individually identifiable, determines that the data is not individually identifiable

Yes  No

**10.7 If your research study requires access to an MHS information system, please indicate the system to obtain data:**

If you do not know which system(s) contain the data elements you need, refer to the Guide for DoD Researchers on Using MHS Data or seek guidance from an MHS data expert:

**PHI Systems:**

MHS Information System	Requesting Data
	
	

**PII-Only Systems:**

MHS Information System	Requesting Data

No records have been added

**De-Identified Data & Other Systems:**

Information System	Requesting Data
Expense Assignment System	
List other system(s):	
List other system(s):	

**10.8 Do you intend to merge or otherwise associate the requested data with data from any sources outside of the MHS, including other DoD systems that are not part of the MHS?**

- Yes, will merge data
- No, will not merge data

**10.9 Indicate the categories of data that you will request from MHS systems or MHS health care providers about research participants or relatives, employers, or household members of the research participants.**

Data Element(s)	MHS	Non-MHS Systems
1. Names		
2. Postal address with only town, city, state and zip code		
3. Postal address with all geographic subdivisions smaller than a state, including street address, city, county, precinct, zip code and their equivalent geocodes, except for the initial three digits of a zip code if, according to the current publicly available data from the Bureau of Census: 1) the geographic unit formed by combining all zip codes with the same three initial digits contains more than 20,000 people; and 2) the initial three digits of a zip code for all such geographic units containing 20,000 or fewer people is changed to 000		
4. Dates including all elements (except year) directly related to an individual, including birth date, admission date, discharge date, and date of death		
5. Ages over 89 and all elements of dates (including year) indicative of such age,		

unless you will only request a single category of "age 90 or older"		
6. Telephone numbers		
7. Fax numbers		
8. Electronic mail addresses		
9. Social Security numbers (SSNs)		
10. Medical record numbers		
11. Health plan beneficiary numbers		
12. Account numbers		
13. Certificate/license numbers		
14. Vehicle identifiers and serial numbers, including license plate numbers		
15. Device identifiers and serial numbers		
16. Web Universal Resource Locators (URLs)		
17. Internet Protocol (IP) address numbers		
18. Biometric identifiers, including finger and voice prints		
19. Full-face photographic images and any comparable images		
20. Any other unique identifying number, characteristic, or code (DEERS ID, EDIPN, Rank)		

If you are obtaining SSNs, provide a justification as to why and explain why a substitute cannot be used

Collecting the SSN of participants allows investigators to order required lab tests in CHCS; also required for subject payment thru Henry Jackson Foundation.

**10.10 Is it possible that the data will become identifiable because of triangulation, a small cell size, or any unique data element(s)?**

Triangulation means using different data elements that are not themselves identifiable but that when combined can be used to identify an individual. For example, triangulation would be using rank and race together to determine the identity of an individual with a particular health condition

Small cell size means that there are only a small number of eligible individuals that satisfy the category description. Guidance for acceptable cell size is available from the Centers for Medicare and Medicaid Services. For example, the rank category of four star generals with a particular diagnosis may be less than 30 so the rank category may need to be expanded to include lower ranks

A unique data element includes any unique features that are not explicitly enumerated in the categories of data in rows 1 – 19 of Table 1 above, but that could be used to identify an individual. Examples of unique data elements include: 1) a unique number, such as a medical record number or EDIPN; 2) a unique code, such as a diagnosis code or a bar code on an electronic health record; and 3) any unique characteristic, such as the rank of general or admiral, or a race or gender combined with another unique characteristic

- Yes, there is a reasonable possibility the data will become identifiable
- No, there is no reasonable possibility the data will become identifiable

**10.11 HIPAA Privacy Rule and Use of Protected Health Information in Research:**

- N/A – will not use or disclose protected health information (PHI)
- HIPAA Authorization will be obtained
- Use of a limited data set where a data use agreement will be obtained
- Waiver/alteration of HIPAA Authorization is being requested

**10.12 Managing Data (Data Management and/or Sharing Plan ) and/or Human Biological Specimens for this Study:**

Include in this section the plan for acquiring data (both electronic and hard copy), access during the study, data/specimen storage and length of time stored, shipment/transmission, and the plan for storage and final disposition at the conclusion of the study. Describe any data agreements in place for accessing data within and/or outside of your institution (e.g., Data Sharing Agreement, Data Use Agreement, Business Agreements, etc.)

See Legacy Protocol

**10.13 Managing Data (Data Management and/or Sharing Plan) and/or Human Biological Specimens for Future Research:**

If the study involves collecting, storing, or banking human specimens, data, or documents (either by the Investigator or through an established repository) for FUTURE research, address. How the specimens /data will be used, where and how data/specimens will be stored (including shipping procedures, storage plan, etc.), whether and how consent will be obtained, procedures that will fulfill subjects' request as stated in the consent, whether subjects may withdraw their data/specimens from storage, whether and how subjects may be recontacted for future research and given the option to decline, whether there will be genetic testing on the specimens, who will have access to the data/specimens, and the linkage, the length of time that data/specimens will be stored and conditions under which data/specimens will be destroyed

See Legacy Protocol

**11.0 Statistical/Data Analysis Plan**

**11.1 Statistical Considerations:**

List the statistical methods to be used to address the primary and secondary objectives, specific aims, and/or research hypotheses. Explain how missing data and outliers will be handled in the analysis. The analysis plan should be consistent with the study objectives. Include any sub-group analyses (e.g., gender or age group). Specify statistical methods and variables for each analysis. Describe how confounding variables will be controlled in the data analysis

### 5.7.1 Data Analysis Table

Independent Variable / Predictor	Dependent Variable/ Outcome	Statistical Test
Riluzole/placebo	PTSD anxiety symptomatology (CAPS total score)	t-test/Mann-Whitney U test
Riluzole/placebo	Clinical Response Rate	Pearson's chi-square test, Fisher's exact test
Riluzole/placebo	Effects of treatment status longitudinally	Regression Analysis
Riluzole/placebo	Origin, gender, age, dose level, illness characteristics	ANOVA, Mantel-Haenszel common odds ratio test, Breslow-Day test
Riluzole/placebo	NAA/Cr ratio	t-test/Mann-Whitney U test
Not Applicable	Not Applicable	Descriptive Statistics

## 11.2 Sample Size Estimation:

A power analysis confirms the study will be able to detect a 9 point change in CAPS score in subjects receiving riluzole augmentation versus placebo using a sample size of 50, assuming a two-tailed test, an  $\alpha = 0.05$ , and a standard deviation of 15 (based on the PI's experience in this population seeking treatment at WRNMMC). This yields a power of 0.844. Power increases to 0.909, under the same assumptions, when a single-tailed test is used. The difference value of 9 is considered the minimally clinically significant difference and is supported by recent publications (Krystal et al, 2013; Schnurr et al, 2001; Weathers et al, 2001; Fontana et al, 1997; Norman et al, 2003; Lunney et al, 2007).

The SAS System  
 The POWER Procedure  
 Two-Sample t Test for Mean Difference  
 Fixed Scenario Elements  
 Distribution Normal  
 Method Exact  
 Number of Sides 2  
 Mean Difference 9  
 Standard Deviation 15  
 Group 1 Sample Size 50  
 Group 2 Sample Size 50  
 Null Difference 0  
 Alpha 0.05

Computed Power  
 Power 0.844

The SAS System  
 The POWER Procedure  
 Two-Sample t Test for Mean Difference  
 Fixed Scenario Elements  
 Distribution Normal  
 Method Exact  
 Number of Sides 1  
 Mean Difference 9  
 Standard Deviation 15  
 Group 1 Sample Size 50  
 Group 2 Sample Size 50  
 Null Difference 0  
 Alpha 0.05

Computed Power  
 Power 0.909

To allow for ineligibility (30-40%) and the possibility that more participants will be needed from

WRNMMC (~2:1 ratio), a total of up to 158 participants will be consented study-wide, with up to 104 participants recruited at WRNMMC.

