**Is this a multi-site study (i.e. Each site has their own Principal Investigator)?**

No

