Subjects will also complete the screening visit where they will be evaluated for study entry and enrollment. Psychiatric history and diagnosis will be administered by study staff at each site using the SCID-P (First et al., 1995) and the DSM-IV Diagnostic Criteria (American Psychiatric Association, 1994). Patients who meet DSM-IV criteria for PTSD must have a Clinician Administered PTSD Scale (CAPS) of 40 at Visits 1 and 2 to be included in the study. Those entering the study at the completion of a referring INTRuST or other medication trial for PTSD will also receive a CGI assessment, and must have a score indicating "NOT improved" or "NOT very much improved" on the CGI scale at the completion of their medication trial to be eligible. The screening visit will include the screening tests, patient history, and psychiatric and physical examinations, as well as menstrual history in females. Subjects will undergo a physical exam, supine and standing vital signs, complete blood cell counts (CBC) with differential, electrolytes, thyroid function test, liver function tests, fasting blood sugar, hematology profile, urinalysis (including screens for substances of abuse), hepatitis screen, SCID, and CAPS. Women of childbearing capacity will have a baseline serum  $\beta$ -HCG. A positive  $\beta$ -HCG will exclude them from participating in the study. Subjects must also have a negative Human Immunodeficiency Virus (HIV) test. Results of these tests will identify patients who should be excluded because of active medical problems or substance abuse that might affect the clinical phenomenology or treatment response and to identify conditions that might make randomization into one of the treatment arms less safe. The CGI will be used to collect information on overall improvement, and the UKU side effect rating scale will be used to collect information on side effects. Finally, eligible subjects who consent to participate in the baseline  $^1\text{H}$  MRS portion of the study will undergo the scan during the screening visit.

The time commitment for the telephone confirmation is estimated to be 10 minutes. The screening visit will take 4 hours. The time commitment for the baseline  $^1\text{H}$  MRS scan is estimated to be 60-90 minutes.

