### 11.3 Data Analysis Plan:

**Primary Analysis:** *(Hypothesis 1) Subjects with PTSD randomized to acute therapy with Riluzole will have a superior response rate acutely compared to subjects randomized to placebo.*

The PI will be primarily responsible for data analysis in this study. He will be assisted by a data analyst or analysts within the Department of Psychiatry at USUHS and this person (or persons) will be added to the protocol as investigators (with IRB approval) prior to any handling of the data. The primary intent of this study is to compare the efficacy of riluzole relative to placebo in the treatment of overall anxiety symptomatology of subjects who have PTSD. This will be analyzed by comparing reductions from baseline scores on the CAPS total score after up to 8-weeks of double-blind therapy to the original score before the start of therapy using t-tests or Mann-Whitney U tests when assumptions for t-tests are not satisfied.

In addition to utilizing the CAPS continuous score, scores will also be dichotomized to examine clinical responders versus non-responders in the treatment and placebo groups. A responder will be defined as any patient who demonstrates a 30% or greater decrease in CAPS total score from baseline (phase I) to the last measured value of Phase II. Response rate analyses will then be performed by comparing the proportion of subjects in each treatment group who met the response criteria. Response rates will be analyzed using Pearson's chi-square test or Fisher's exact test when expected cell sizes are less than 5.

In order to more thoroughly assess the effects of treatment status in a longitudinal setting, random effects regression will also be used to examine the study groups over time in the presence of additional covariates.

In general, variables that are continuous, yet non-normally distributed, will be appropriately transformed or will be analyzed using appropriate non-parametric tests. Variables that are non-continuous (ordinal, nominal) will be analyzed using appropriate non-parametric tests. All tests of hypotheses will be tested at a two-sided a level of 0.05.

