All subjects will be evaluated for study entry during the Screening Visit by a Masters-level Clinical Research Psychologist under the supervision of a credentialed provider within the WRNMMV Behavioral Health Clinic using a CAPS assessment; WRNMMC study research staff will recruit, screen, consent and enroll subjects at WRNMMC, while Syracuse VA Medical Center study research staff will recruit, screen, consent and enroll subjects at the Syracuse VA Medical Center, as well as from associated community-based outpatient clinics (CBOCs). CAPS score  $\geq$  40 will be necessary for study enrollment. Those entering the study at the completion of an INTRuST medication trial will also receive a CGI assessment, and must have an assessment determination of "NOT improved" or "NOT very much improved" on the CGI at the completion of their medication trial to be eligible for study enrollment.

The Screening Visit will include all screening tests, patient and family history, and psychiatric and physical examinations, as well as menstrual history in females. Inclusion and exclusion criteria will be assessed. Subjects will undergo a physical exam, supine and standing vital signs, blood chemistries, liver function tests, hematology profile, urinalysis (including screens for substances of abuse), hepatitis screen, SCID, and CAPS. Women of childbearing capacity will have baseline serum  $\beta$ -HCG, and a positive  $\beta$ -HCG will exclude them from participating in the study. Subjects must also have a negative Human Immunodeficiency Virus (HIV) test.

A complete medication list will be compiled prior to dispensing riluzole and verification of the list for change will be done at the weekly clinical visit to assess for compounds that may interact with clearance of the drug.

Participants will be advised to take riluzole 1 hour before or two hours after meals for optimal metabolism of the compound. Education will be provided that the bioavailability of the compound is significantly affected by high fat meals and that charbroiled food may increase the speed of clearance of the compound from their bodies.

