### **14.3**

#### **Confidentiality Protections (for research records, data and/or specimens):**

Describe in detail the plan to maintain confidentiality of the research data, specimens, and records throughout the study and at its conclusion (e.g., destruction, long term storage, or banking). Explain the plan for securing the data (e.g., use of passwords, encryption, secure servers, firewalls, and other appropriate methods). If data will be shared electronically with other team members/collaborators outside the institution, describe the method of transmission and safeguards to maintain confidentiality. Explain whether this study may collect information that State or Federal law requires to be reported to other officials or ethically requires action, e.g., child or spouse abuse

i. The Principal Investigator at each site maintains adequate and accurate records in order for the conduct of the study to be fully documented and study data subsequently verified. All records pertaining to the identity of the subjects will be kept private and confidential. For documentation containing personal identifying information that is to be retained locally, on-site, it will be maintained in a locked file cabinet. After study closure, Investigators retain all source documents and study-related documents pertinent to protocol compliance. Because the length of time required for retention of records depends upon a number of regulatory and legal factors, Investigators will store documents until they receive notification that documents can be destroyed. In general, study records are retained and securely stored for a minimum of 7 years after the completion of all study activities.

ii. When will you destroy the research source documents, data file, and the master code?

In general, study records are retained and securely stored for a minimum of 7 years after the completion of all study activities.

iii. Will research data including Identifiable Protected Health Information be sent outside of WRNMMC?

Yes – Please explain assurances you have received from the outside party that they will appropriately follow confidentiality protections, follow the HIPAA requirements, and abide by the provisions of your Authorization.

No

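### Two sites enrol, but the primary CAPS comparison and the response comparison have no site term; adding one is a modest, nearly free gain in precision

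*Combined protocol and SAP*

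**What the plan says.** Section 11.2 sets a ceiling of 158 consented participants and describes a split of about 2:1 towards WRNMMC as a possibility: "participants will be consented study-wide, with up to 104 participants recruited at WRNMMC". Section 13.2 has local staff recruit and consent at WRNMMC, "while Syracuse VA Medical Center study research staff will recruit, screen, consent and enroll subjects at the Syracuse VA Medical Center" and from its associated outpatient clinics.

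For the primary outcome, Table 5.7.1 gives "t-test/Mann-Whitney U test" with riluzole/placebo as the only predictor, and 11.3 describes the same test on change from baseline in CAPS total. Response is compared by Pearson's chi-square or Fisher's exact test, also without site. Section 11.3 adds that "All tests of hypotheses will be tested at a two-sided a level of 0.05".

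Two items come close to site. Section 11.3 adds a random effects regression with covariates that it does not name, as a supplementary analysis. It also lists origin, undefined, among the secondary subgroup factors. Neither puts site in the primary test. Section 9.5 gives 1:1 randomisation and, in the text available, does not mention stratification by site.

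**The concern.** A military hospital and a VA centre with outpatient clinics may see different patients and different average CAPS change over 8 weeks. If so, part of the variation in the primary outcome is explained by a variable that is known for everyone and that the test ignores. Under simple randomisation, the chance difference between arms in their share of Syracuse patients then adds noise to the treatment estimate. Under allocation blocked by site, that noise is absent from the estimate, but the unadjusted standard error still counts it, so the test is conservative. In both cases some precision is given up, and a term for site would recover it.

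**Working it through.** **Inputs.** Difference 9, SD 15, 50 per arm, two-sided alpha 0.05 (11.2, 11.3). Site split: 158 − 104 = 54; 104/54 = 1.93; 104/158 = 66%. The ceilings refer to consented participants. I assume the same split among 100 randomised, so 66 at WRNMMC and 34 at Syracuse. The site difference in mean CAPS change, D, is not in the documents; I take 0 to 12 points.

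**The plan's own figure.** The standard error is 15 × √(2/50) = 3.0, so the noncentrality is 9/3.0 = 3.0 with 98 degrees of freedom. Power is 0.8439. Section 11.2 states "This yields a power of 0.844", so the figure reproduces.

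**Chance imbalance without stratification.** The number of Syracuse patients in one arm has mean 17 and variance 50 × 0.34 × 0.66 × 50/99 = 5.67, so SD 2.38 (95% range 12 to 22). The between-arm difference in Syracuse share has SD 2 × 2.38/50 = 0.095. The chance shift in the unadjusted estimate therefore has SD 0.095 × D: 0.5 CAPS points at D = 5, 0.8 at 8 and 1.1 at 12, against the standard error of 3.0.

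**Cost of a site term when D = 0.** One degree of freedom (97 instead of 98) takes power from 0.8439 to 0.8438. Chance imbalance inflates the variance by 1/(1 − r²), where r is the treatment-site correlation; the mean over the hypergeometric distribution is 1.010. Average power becomes 0.840, a cost of 0.4 points.

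**Break-even.** Site explains 0.34 × 0.66 × D² = 0.2244 D² of the variance. This offsets the 1.04% inflation when 0.2244 D²/225 = 0.0104, that is at D = √(0.0104 × 225/0.2244) ≈ 3.2.

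**Power over the assumed range.** Reading A holds total SD at 15, so the within-site SD is √(225 − 0.2244 D²). Reading B takes 15 as the within-site SD, so the total SD is √(225 + 0.2244 D²). Reading B is plausible because 11.2 draws the SD from the WRNMMC population alone. The powers are noncentral t, with the adjusted ones averaged over chance imbalance. Simulation of both tests agrees to within about 0.002.

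| D | A: unadjusted | A: with site | B: unadjusted | B: with site |
|---|---|---|---|---|
| 0 | 0.844 | 0.840 | 0.844 | 0.840 |
| 3 | 0.844 | 0.843 | 0.841 | 0.840 |
| 5 | 0.844 | 0.849 | 0.835 | 0.840 |
| 8 | 0.844 | 0.863 | 0.821 | 0.840 |
| 12 | 0.844 | 0.891 | 0.793 | 0.840 |

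**Type I error.** Under simple randomisation the simulated error rate is 0.048 to 0.051 with or without the site term. Under allocation blocked by site, with total SD 15, the unadjusted test rejects at about 0.043 at D = 8 and 0.034 at D = 12. The site term restores 0.05.

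**The case against.** The strongest reply is that nothing is broken. The unadjusted t-test keeps its error rate under simple randomisation, and with total SD 15 it delivers the stated power whatever the site difference. The gains depend on assumed values of D, and 8 and 12 points are close to or above the whole 9-point treatment effect. At 5 points or less the gain is at most about half a power point. All of that stands.

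It can also be said that site may be covered already, through origin, through the unnamed covariates, or through stratified allocation in the legacy protocol to which several sections defer. The first two are secondary or supplementary and leave the primary test unchanged. The third cannot be excluded, so I make no claim that stratification is absent. If allocation is stratified, the case for the site term remains, because the unadjusted test is then conservative.

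A reader might infer more than the documents support:

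- *That each site has its own CAPS raters.* Section 9.5 says "Psychiatric history and diagnosis will be administered by study staff at each site", but that concerns diagnosis. The same section assigns ongoing assessment, and 13.2 assigns the entry CAPS of all subjects, to a Masters-level psychologist supervised within the WRNMMC clinic. The text is mixed. In addition, the outcome is a change score, so a constant rater offset between sites cancels.
- *That the multi-site answer on the form is evidence of an analysis flaw.* The form asks "Is this a multi-site study (i.e. Each site has their own Principal Investigator" and is answered no, while 14.3 says "The Principal Investigator at each site maintains adequate and accurate records". The wording is in tension, but this is administrative and has no bearing on the test.
- *That adjustment costs nothing or removes imbalance.* It has the small cost shown above, and it corrects the estimate for imbalance. Only stratified allocation limits the imbalance itself.

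**Conclusion.** The point holds as a modest precision improvement. The primary CAPS comparison and the response comparison omit site although two sites enrol. The result is not biased and the error rate is not inflated; a reading of this as a validity error is not supported.

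For CAPS change, a site term changes power by −0.4 points if the sites do not differ, and by about +0.5, +2 and +5 points at assumed differences of 5, 8 and 12, with total SD 15. If 15 is the within-site SD, the term does not raise power above plan but keeps it near the stated 0.844, where the unadjusted test falls to about 0.82 at 8 points.

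These figures rest on 100 randomised, a 66:34 split carried over from the consent ceilings, equal SD at both sites, and the same treatment effect at both. The size of any site difference is unknown from the documents.

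**What to change.** In 11.3 and Table 5.7.1:

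- Make the primary analysis a linear model of CAPS change with treatment and site as fixed factors. Define site as two levels, with the Syracuse outpatient clinics counted under Syracuse.
- Replace the Mann-Whitney U fallback, which cannot take a site factor, with the van Elteren test (its site-stratified form).
- Compare response by a Cochran-Mantel-Haenszel test stratified by site.

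It would also help to state whether the allocation list is stratified by site and who rates CAPS at Syracuse.

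The cost is a few lines of text, one degree of freedom, and about 1% expected variance inflation (up to 0.4 power points) if the sites do not differ. No new data are needed, since the enrolling site is known for each participant, and the required sample size does not change materially.
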